### **11.2.1.3 Sustained Headache Pain Free**

Sustained pain-free response will also be summarized at the 24 and 48-hour post-dose time points in the same tables of Headache pain free for listed populations in section 11.2.1.1

Sustained Pain-Free is defined as experiencing headache pain-free at two hours after first dose and at the subsequent indicated assessment time, having not used any medications after the first dose for each treated migraine.

This data will be summarized for the 1st, 2nd, 3rd, 4th, 5th, 10th, 15th, and 20th treated migraine.

### **11.2.1.4 Consistency Analyses**

This analysis will be performed on ITT subject level population.

For subjects that treated 3 or more migraines, headache pain-free at 2 hours, headache relief at 2 hours and MBS free at 2 hours will be summarized across the first three treated migraines with headache severity assessments. The number and percentage of subjects reaching pain-freedom and pain relief will be reported for the following categories: 0 of 3 migraines meeting the criteria, 1 of 3 migraines meeting the criteria, 2 of 3 migraines meeting the criteria, 3 of 3 migraines meeting the criteria, and 2 or 3 of 3 migraines meeting the criteria.

#### **11.2.1.5 Presence of Migraine Symptoms**

Counts and percentages of the presence of associated symptoms will be presented at the 0.5, 1, 2, 4, 24, and 48-hour post-dose time points. These will be summarized by treatment group for the ITT population and ITT-2nd dose rescue and recurrence populations based on second dose at treated migraine level for each treated migraine attack.

The presence of the following associated symptoms will be presented based on the response to the presence of that symptom at that time point.

- Nausea
- Phonophobia
- Photophobia
- Vomiting

This data will be summarized overall and for the 1st, 2nd, 3rd, 4th, 5th, 10th, 15th, and 20th treated migraine.

#### **11.2.1.6 Headache Pain Relief**

Counts and percentages of the number of subjects with headache relief will be presented at the 0.5, 1, 2, 4, 24, and 48-hour post-dose time points. This summary will be presented by treatment group for the ITT population, ITT-2nd dose rescue and recurrence populations based on second dose at treated migraine level for each treated migraine attack.

Headache relief is defined as experiencing a moderate (2) or severe (3) headache at baseline which becomes mild (1) or none (0) at the summarized time point, or a mild (1) headache at baseline which becomes none (0) at the summarized time point for each treated migraine.

Treated migraines without a headache severity at baseline will be excluded. Treated migraines missing a severity assessment at a post-dose time point will not be categorized as pain relief.

This data will be summarized for the 1st, 2nd, 3rd, 4th, 5th, 10th, 15th, and 20th treated migraine.

For subjects that treated 5 or more migraines, headache pain relief at 2 hours will be summarized across the first five treated migraines and as overall response for all treated migraines.. Overall response for each subject in this subgroup is calculated by dividing the number of successful responses (responses at 2 hours) by total number of attacks treated.

Additionally, a time to headache pain relief Kaplan-Meier analysis will be conducted on the first treated migraine for the subject-level ITT population by dose.

Summary of headache pain relief will be presented for all treated migraine attacks for ITT population as overall numbers and by each quarter as defined in section 8.5.

#### **11.2.1.7 Disability**

Counts and percentages of the level of disability will be presented at baseline and at the 0.5, 1, 2, 4, 24, and 48-hour post-dose time points. These will be summarized for the ITT population, at treated migraine level each treated migraine attack by treatment group.

Disability is measured on a four-point scale.

- Not at all (0)
- Mild interference (1)
- Marked interference (2)
- Completely, needs bed rest (3)

Data will be presented based on the 4 levels of the scale, as ‘Not at all’ versus all other categories, and as ‘Not at all’ or ‘Mild interference’ versus ‘Marked interference’ or ‘Completely, needs bed rest’. Additionally, a shift table of baseline disability versus 2 hour post-dose disability will be presented

This data will be summarized for the 1st, 2nd, 3rd, 4th, 5th, 10th, 15th, and 20th treated migraine.

#### **11.2.1.8 Patient Global Impression of Change**

Counts and percentages of the level of patient global impression of change (PGIC) will be presented by treatment group at the 2-hour post-dose time point. These will be summarized for the ITT population, at treated migraine level each treated migraine attack by treatment group.

Patient global impression is measured on a seven-point scale.

- Very much better
- Much better

- A little better
- No change
- A little worse
- Much worse
- Very much worse

This data will be summarized for the 1st, 2nd, 3rd, 4th, 5th, 10th, 15th, and 20th treated migraine.

Data will also be presented in 2 categories, comparing those who indicated “Very Much Better” or “Much Better” to those who reported being “A little better” or “No change” or “A Little Worse” or “Much Worse” or “Very Much Worse”.

## **12 SAFETY ANALYSIS**

This section details the specifications for summarizing safety endpoints.

Adverse event (AE) analyses will be presented on the Safety populations.

Laboratory, vitals, ECG, Physical examination and C-SSRS analyses will be presented on the Safety population.

Safety endpoints will be summarized using descriptive statistics.

Descriptive statistics for quantitative variables will include: n, mean, median, minimum, maximum, and standard deviation. Descriptive statistics for qualitative variables will include frequency counts and percentages. Adverse events will be summarized in terms of the proportion of subjects and the proportion of treated migraine attacks associated with any adverse event and with specific adverse events.

Values for all safety endpoints will also be presented in listings sorted by treatment group and subject.

### **12.1 Adverse Events**

An AE with the date of onset on or within 48 hours after a dose of study drug, or an event that worsens in intensity within 48 hours of a dose of study drug will be considered a treatment-emergent adverse event (TEAE). Other AEs are defined as those occurring after randomization but not considered to be treatment-emergent.

Descriptive statistics for both number of subjects ever experiencing an event as well as for the total number of events will be presented. Furthermore, descriptive statistics will also be calculated for each treatment group irrespective of first or second dose for AE relationship and AE severity. If multiple intensities are reported for a given AE and subject, then the most severe intensity will be counted. A separate, similar analysis will be conducted for TEAEs.

AEs with a missing start date will be assumed to be treatment-emergent, except in situations described in Appendix 1. If a subject takes at least one dose of study drug, but the date and time of dosing is missing in the e-diary, all AEs for that subject will be considered treatment-emergent, if the AEs occur between available date of dosing as recorded only in CRF for up to 48 hours (2 days) post recorded date of dosing. If the date and time of the second dose is missing in e-diary then all AEs for that subject will be considered as treatment emergent due to second dose, if AEs occur between available date of dosing in CRF for second dose, and an ending boundary of 2 days after recorded date of dosing with second dose, inclusive. See Appendix 1 for derivations related to partial dates and times.

Nausea and/or vomiting reported as adverse events during a migraine by any subject that also noted these as characteristics of their migraine will be presented by treatment groups and not be considered related to treatment but rather an underlying condition of the migraine.

AEs will be coded by the Medical Dictionary for Regulatory Activities (MedDRA) version 21.0.

Unless otherwise stated, frequencies of adverse events will be displayed by applicable treatment group and overall. AEs will be sorted alphabetically by system organ class (SOC), preferred term (PT), and frequency. For the overall summary of AEs, both total subjects ever experiencing an event as well as total number of events will be presented. For all other summaries, subjects with multiple occurrences of the same AE preferred term will be counted once within the corresponding system organ class and preferred term.

Adverse events will be summarized by treatment arm in the following tables:

- Overall summary of AEs for Safety Population, 6-month, and 12-month population including:
  - All AEs
  - TEAEs
  - Other AEs
  - Related TEAEs
  - AEs leading to study discontinuation
  - Serious AEs
  - Related serious AEs
  - Deaths

- Incidence of All AEs and Other AEs by SOC for the Safety Population and Pre-administrative hold Population.
- Incidence of TEAEs by SOC for the Safety Population, 6 month and 12 month Safety Population.
- Incidence of TEAEs by decreasing frequency of PT for the Safety Population and Pre-administrative hold Population.
- Incidence of TEAEs occurring in more than 2% of subjects by quarter for Safety Population.
- Incidence of TEAEs and SAEs by SOC, PT and Doses for the Safety Population, 6-month and 12-month Safety Population.
- Summary of TEAEs by SOC, PT, and migraine attack sequence for the Safety Population.
- Summary of TEAEs by PT and migraine attack sequence for subjects that treated 5 or more migraine attacks in the Safety Population
- Summary of TEAEs occurring in more than 2% of subjects by PT for the Safety Population.
- Incidence of all SAEs by SOC for the Safety Population, 6 month and 12 month Safety Population.
- Incidence of All AEs leading to study discontinuation for Safety Population, 6-month and 12-month Population.
- Listing of All AEs leading to study discontinuation or death.
- Incidence of serious TEAEs for Safety Population, 6-month and 12-month Population. In addition, listings of these will be presented for Pre-Administrative Hold Population.
- Listing of Serious AEs.
- Time to onset and duration of TEAEs occurring in more than 2% of subjects relative to dosing regardless of second dose. If the time of adverse event is missing, no imputation will be performed for this presentation. The most frequent TEAE list will be finalized before interim soft lock and final database lock.
- Subgroup analysis will be presented for subject with cardiovascular risk factors. TEAE will be compared among subjects with and without CVRF for individual event for Safety population. They will be tested with chi-squared test or fisher's exact test as appropriate with respect to sample size and all comparisons will be done at level of significance of 0.05.

Above tables will be presented for various types of AE criteria as below:

1. Incidence of TEAE table will be provided by-subject analysis. For this analysis, the adverse events will be reported out of total number of subjects in each treatment group regardless of whether a second dose is taken.
2. Similar events as Point #1 will be reported when only 1 dose was taken and additionally when 2 doses were taken.

3. Incidence of serious adverse events table will be reported by-subject analysis for each treatment group regardless of whether a second dose is taken.
4. Similarly, to Point # 2, serious events will be reported when only 1 dose was taken and additionally when 2 doses were taken.
5. TEAEs summary will be provided by each treated migraine analysis. For this analysis, the adverse events will be reported out of total number of treated migraines for each treatment group regardless of second dose.
6. Additionally TEAE by-subject analysis will be provided for treated 1st migraine attack, 2nd migraine attack, 3rd migraine attack, 4th migraine attack, 5th migraine attack, 10th migraine attack, 15th migraine attack, 20th migraine attack
7. Specific most common TEAEs will be reported in descriptive statistics (n, mean, median, SD, Minimum and maximum) by proportion of treated migraines attacks in subjects experiencing the TEAE at least once. This data will be presented out of total number of subjects in each treatment group. TEAEs will be reported if 2% or more of subjects any any treatment group report the event.

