1. Relationship to Study Drug: The Investigator must assess whether they consider an AE to be drug-related. In assessing this relationship, the Investigator must use information about the drug as outlined in the Investigator's Brochure (IB), the subject's pre-existent medical conditions/concurrent medication, and chronology of the event relative to drug administration. The following definitions will be used:
 - **Reasonably or possibly related** applies to those AEs that, after careful medical consideration at the time they are evaluated, are considered by the Investigator (or other qualified physician) to have at least a possible relationship to study drug.
 - **Not reasonably or not possibly related** applies to those AEs that, after careful medical consideration at the time they are evaluated, are considered by the Investigator (or other qualified physician) to have no relationship, or no reasonable possibility of a relationship, to study drug.
2. Event Severity: The Investigator will be asked to assess the severity of the AE using the WHO Toxicity Criteria, as shown in Appendix 1. The WHO criteria assign a grade of 1 through 4 to indicate the severity of AEs. For AEs that are not listed in the WHO criteria, the Investigator will use medical judgment to assess the severity of the AE.

The following are guidelines to be used by the Investigator to judge the event severity of an AE that is not in the WHO Toxicity Criteria:

- Mild - awareness of sign or symptom, but easily tolerated
 - Moderate - discomfort enough to cause interference with usual activity
 - Severe - incapacitating with inability to work or perform usual activity
 - Life Threatening
3. Duration: Start and end dates and times, or if continuing.

4. Action taken.
5. Whether it constitutes a SAE, per definition below.
6. Outcome: resolved, resolved/ with sequelae, continuing, death, or unknown (only for subjects that are lost to follow-up).

The investigator (or designee) should attempt to establish a diagnosis of the AE based on the sign, symptoms and/or other clinical information. In such cases, the diagnosis, and not the individual signs/symptoms or laboratory abnormalities should be documents in the subject's source documentation and the CRF unless the etiology of the event is unknown. An assessment should be made at each visit (or more frequently if necessary) of any changes in severity, the suspected relationship to study drug, the interventions required to treat it and the outcome.

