## 2 SUMMARY OF THE CLINICAL TRIAL PROTOCOL

### 2.1 Study Summary

This is a prospective, randomized, open-label study in subjects with migraine who have completed COL MIG-301/H8H-CD-LAHJ or COL MIG-302/H8H-CD-LAHK. Subjects will be stratified (yes or no) for use of concomitant medications that reduce the frequency of migraine episodes.

Subjects will be asked to treat all migraine attacks with study drug on an outpatient basis for up to 12 months. Each subject's study participation will consist of a screening visit (Visit 1) and a treatment period of up to 12 months during which the subject will treat all migraine attacks with either lasmiditan 200 mg or lasmiditan 100 mg (with a second dose permitted between 2 and 24 hours (h) for rescue or recurrence of migraine). During the treatment period subjects will return to the clinic at 1, 3, 6, 9 and 12 months. There will be an early termination (ET) visit within two weeks (14 days) of treatment discontinuation for all subjects that discontinue between scheduled visits. The End-of-Study (EoS) visit will be at 12 months or at any scheduled visit when the subject's participation in the study is ended. Participation in the study for 6 months will be defined as completing **Month 6/Visit 4**. Participation in the study for 12 months will be defined as completing **Month 12/Visit 6** (not including early termination subjects).

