2. If CRF dates data is NOT matched with e-diary dates: CRF dates will be compared with e-diary dates and times for possible and reasonable match. If CRF dates appear to be out of order i.e. second dose date and/or time recorded in e-diary is before first dose date and/or time; same first and second dose dates and time in e-diary, such dates and/or time will not be corrected by CRF data as provided by the subject due to unavailability of times of dosing in CRF. In such cases, if the CRF dates and e-diary dates do not match, then for overall treatment exposure, earliest date available from CRF or e-diary will be considered for start of exposure and latest date available from CRF or e-diary will be considered for end of exposure. Additionally, for first dose exposure, earliest date available from CRF or e-diary will be considered for start of exposure of first dose and latest date will be considered for end of exposure of first dose. Similarly, for second dose exposure, earliest date available from CRF or e-diary will be considered for start of exposure of second dose and latest date will be considered for end of exposure of second dose.
3. If CRF dosing dates are available but e-diary dosing information is missing: CRF dosing date will be determined as confirmation of dosing at sites even if subject could not enter dosing information in e-diary due to any reason. These subjects data will be used for analysis. If the first dose date is available in CRF but missing from e-diary then eligibility date will be used as the first alternative and the randomization date will be used as second alternative. If the second dose date is available in CRF but missing from e-diary then study completion/discontinuation date will be used as the alternative. Additionally, for CRF dosing dates which are partial dates, missing dates and dates which fall outside the visit window, reported visits windows with respect to reported CRF dosing dates windows will be used for treatment start and end dates.

4. If CRF dosing dates are NOT available but e-diary dosing information is available: It will be determined that these subjects have not confirmed this dosing at the site (or are lost to follow-up) and there is no confirmation on exact dosing on CRF. These unconfirmed migraines will be excluded from safety analyses.

The statistical evaluation will be performed using SAS version 9.4 or higher.

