4. Subjects reporting migraine start time or dosing time in future in e-diary. If a subject reports a migraine start time in the future and if the time reported is less than one hour in the future, this will be considered as minor minute or hour entry issues and the migraine start time will be set as time of collection. The remaining time issues will be assumed on visual confirmation as AM/PM (midnight/noon) and PM/AM (yesterday/today) entry issues then these will be rolled back by increments of 12 hours until the time is before time of data collection. After these corrections if migraine start

is still after dosing time then the migraine start time is set to dosing time. These subjects will be included in the appropriate populations of efficacy analysis with these assumptions.

1. Similarly for subjects who report a first dose time with start in the future (by several hours) than indicated dosing with question “Treating Migraine with Study Med now” as “Y” at the migraine pain begin time, their efficacy assessments for first dose will be those many hours ahead of the actual assessment time for severity reporting. For example, e-diary’s 0.5 hour time point is actually 7.5 hours if the first dose time is after 7 hours of the reported migraine start time. If the reported dose time is less than 10 minutes than the time of reporting migraine as in the stated question, then these will be ignored and subject’s efficacy assessments will be used for appropriate populations of efficacy analysis. All other subjects with time difference of greater than 10 minutes will be excluded from the appropriate populations of efficacy analysis.
5. Subjects with partial second dose time on CRF and no e-diary date and time for second dose Subjects who are able to enter the first dose assessment data in e-diary but they are not able to complete the e-diary for second dose. These subjects will be able to give second dose confirmation date on the CRF at site for visit 2 but may not remember the time of the dosing for second dose after first dose. These subjects will be considered in the appropriate populations of efficacy analysis for first dose available assessments based on the assumption that they took the second dose after the minimum of 2 hours post first dose. For these subjects any assessments for first dose data after 2 hours will be unscheduled and not be summarized.

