#### 16.5 DATA HANDLING RULES OF EFFICACY AND EXPLORATORY ANALYSIS FOR E-E-DIARY AND CRF DATES AND TIMES

As described in Section 5.4, Scenario #6 subjects will be included in efficacy analysis with respect to e-diary dates and times and their relative post-dose assessments times under below rules if their respective CRF date does not match.

Subjects with partial dates entered on CRF with missing time of dosing for first dose on CRF that do not contradict the e-diary date. These subjects will be considered for efficacy analysis with respect to e-diary date and time.

Subjects with CRF first dose date is after subject answered the question for 0.5 time point due to which the questions in the e-diary look appropriate with respect to e-diary first dose date. These subjects will be considered for efficacy analysis with respect to e-diary date and time.

Subjects with indication in CRF that they had taken first dose prior to all migraine start times recorded in e-diary due to which first dose e-diary date becomes closer to or after last migraine start in the e-diary. These subjects will be considered for efficacy analysis with respect to e-diary date and time.

Subjects with different first dose times in e-diary vs on CRF. If the e-diary data is not entered retroactively by subject, then e-diary first dose dates will be in accordance with assessments completed by subject. These subjects will be considered for efficacy analysis with respect to e-diary date and time.

Subjects with CRF dates for 2nd dose are entered more than 24 hours after first dose. These subjects will be considered for efficacy analysis with respect to e-diary date and time.

Subjects with indication in CRF that they had taken second dose prior to all migraine start times recorded in e-diary due to which second dose e-diary date becomes closer to or after last migraine start in the e-diary. These subjects will be considered for efficacy analysis with respect to e-diary date and time.

Subjects with indication of taking second dose on CRF with CRF date and time but second dose date is not in e-diary. Due to this, some first dose data from e-diary assessments before time of second dose on CRF will be used for analysis. These subjects' first dose data will be considered for efficacy analysis with respect to e-diary date and time.

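### SAP 12.1: when the e-diary lacks the second-dose time, a date-only CRF entry makes AEs that began before the second dose count as due to it

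*SAP*

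**What the plan says.** SAP 12.1 has a special rule for a second dose whose date and time is missing in the e-diary. In that case "all AEs for that subject will be considered as treatment emergent due to second dose". The rule works only inside a window. Its opening is worded "if AEs occur between available date of dosing in CRF for second dose"; it closes at "an ending boundary of 2 days after recorded date of dosing with second dose, inclusive". Both limits are calendar dates. Neither the first-dose time nor the AE onset time is used.

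The SAP is not consistent on whether the CRF holds a dosing time. Section 5 (Safety Analysis, item 2) declines to correct out-of-order diary entries from the CRF "due to unavailability of times of dosing in CRF". Elsewhere in section 5, CRF dates and times are to be completed for all subjects. Appendix 16.5 has a scenario that begins "Subjects with indication of taking second dose on CRF with CRF date and time but second dose date is not in e-diary".

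Four other places bear on the point:
- SAP 5.4 limits second-dose analyses to data observed at or after the time of the second dose.
- Appendix 16.2 does not count an AE that starts before the dose date and time as treatment-emergent.
- SAP 5.7, scenario 5, deals for efficacy with a second dose known only from the CRF and assumes that "they took the second dose after the minimum of 2 hours post first dose".
- Protocol 9.2.1 has AE onset recorded to the clock: "Duration: Start and end dates and times, or if continuing".

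**The concern.** The second dose follows the first within a day: SAP 2.1 describes "a second dose permitted between 2 and 24 hours (h) for rescue or recurrence of migraine". Protocol 5.4 keeps the 2 to 24 hour interval but restricts who may take a second dose and for what reason. The two doses will therefore often share a calendar date. If the window opens at midnight on that date, an AE that began between the two doses, or before either, is labelled as due to a dose not yet taken.

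The primary objective (Protocol 5.1) covers the safety of lasmiditan as a first and as a second dose. Protocol 10.5.1 calls for AE counts separated by first and second dose, and SAP 12.1 lists TEAEs and SAEs by SOC, PT and doses. If those tables use this flag, some first-dose events would appear as second-dose events. Missing second-dose times are foreseen: SAP 5.7 describes several ways in which they arise.

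**Working it through.** The plan gives no figure to reproduce; the sample size is not hypothesis-based and AEs are mainly summarised descriptively. The check applies the rule to a timeline and then asks how often it would mislabel an event.

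**1. Timeline (illustrative).** First dose at 09:00 in the e-diary, dizziness at 09:30, second dose at 15:00 known from the CRF by date only.
- SAP 12.1 as written: the window runs from 00:00 that day to the end of the second day after, so 09:30 is inside and the event is due to the second dose.
- SAP 5.4 and Appendix 16.2 with the true time: 09:30 is before 15:00, so it is not a second-dose event.
- The 5.7 scenario 5 assumption: the earliest second dose is 09:00 + 2 h = 11:00, and 09:30 is before that, so again it is not a second-dose event.

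The date window spans 3 calendar days, 3 × 24 = 72 hours, against the 48 hours of the general TEAE rule.

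**2. How often, closed form.** Let *a* be the hours from first dose to AE onset and *g* the hours from first to second dose, with *a* < *g*. Assume that the clock time of the second dose is uniform over 24 hours. The AE then falls on the second-dose date with probability

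P = 1 − (*g* − *a*)/24.

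For *a* = 1 h:

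| Gap *g* (h) | P |
|---|---|
| 2 | 1 − 1/24 = 95.8% |
| 4 | 1 − 3/24 = 87.5% |
| 8 | 1 − 7/24 = 70.8% |
| 12 | 1 − 11/24 = 54.2% |
| 24 | 1 − 23/24 = 4.2% |

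With *g* uniform over 2 to 24 h the mean gap is 13 h, so P averages 1 − (13 − 1)/24 = 50.0%. The same average is 47.9% for *a* = 0.5 h and 54.2% for *a* = 2 h.

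**3. How often, daytime dosing.** This simulation assumes a first dose uniform over 06:00 to 23:00 and AE onset uniform over 0 to 2 h after it. The share of those AEs dated on or after the second-dose date is:

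| Assumed gap (at most 24 h) | Share labelled as due to second dose |
|---|---|
| Uniform over 2 to 24 h | 36% |
| 2 h plus an exponential time, mean 6 h | 63% |
| 2 h plus an exponential time, mean 3 h | 78% |

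The clock-time, onset and gap distributions are all assumptions. For the same uniform gap the two approaches give about 50% and 36%, which shows how far the result depends on them.

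**4. Which outputs use the flag.** The numbered list of AE criteria in SAP 12.1 reports AEs regardless of a second dose (items 1, 3 and 5) or split by one versus two doses taken (items 2 and 4). Relationship and severity are irrespective of dose. In the timeline above, the 09:30 event belongs to a two-dose attack and stays in the two-dose row whichever rule is used. The exposed outputs are the attribution flag itself, the by-dose presentation in Protocol 10.5.1, and the SAP table by SOC, PT and doses if it is built on the flag.

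**The case against.** The strongest reply is that no table in the SAP is shown to depend on the flag. If doses in the table title means only one versus two doses taken, as items 2 and 4 suggest, those tables do not change. That stands, and it limits the point to the flag and to by-dose presentations that use it. It does not make the flag correct, and Protocol 10.5.1 does plan a first-dose versus second-dose presentation.

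Second, a reader might infer that the rule takes these events away from the first dose. The text does not say so: SAP 12.1 never makes attribution exclusive, and an AE 30 minutes after a timed first dose is still a TEAE under the general 48-hour rule. The event may be counted under both doses.

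Third, a reader might infer that the CRF never holds a dosing time. Section 5 and Appendix 16.5 point the other way, so the midnight opening is certain only where the CRF gives a date alone. Even with a CRF time, however, the 12.1 rule is worded on the date.

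Fourth, it is tempting to treat first dose + 2 h as the earliest possible second dose. The SAP itself expects exceptions: 5.4 handles a second dose before the 2-hour time point and 8.5 tabulates second doses taken before the 2-hour assessment. A hard bound could move genuine second-dose AEs to the first dose. This objection stands and shapes the fix.

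**Conclusion.** The point holds as an error of dose attribution. Where the second-dose time is missing in the e-diary and the CRF has only a date, SAP 12.1 labels as due to the second dose AEs that began before it, contrary to SAP 5.4 and the principle in Appendix 16.2.

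A reader might go further and conclude that the primary TEAE results or the overall second-dose AE rate are materially inflated. The documents do not support that. An AE soon after the first dose is a TEAE in any case. Overall counts could change only through AEs that began before the first dose that day, or late in the 72-hour window, and that lie within 48 hours of no dose.

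The 36% to 78% range describes AEs with onset in the first 2 hours, within attacks with a date-only second dose, under assumed timings. It is not a bias in any reported rate, because the number of such attacks is not given. The change is still worth making: it is cheap, and second-dose safety is part of the primary objective.

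**What to change.** Amend the missing-second-dose rule in SAP 12.1 as follows:

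1. If the CRF records a second-dose time, use it.
2. Otherwise, do not attribute to the second dose any AE with onset before the first-dose time.
3. Show AEs with onset from the first dose to first dose + 2 h under the first dose, following 5.7 scenario 5, unless the record indicates an earlier second dose.
4. Attribute later AEs on or after the CRF second-dose date to the second dose, as now.
5. Show AEs with no onset time, or where the first-dose time is also missing, as dose not determinable.
6. List every event whose attribution the new rule changes.

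Also state whether an event can count under both doses, and whether the table by SOC, PT and doses uses this flag or the one-versus-two-dose split. Reconcile the statements on CRF dosing times in section 5 and Appendix 16.5. Section 5, Safety Analysis item 3, also needs reconciling: it substitutes the study completion or discontinuation date when the second-dose date is on the CRF but not in the e-diary.

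The cost is a short SAP paragraph, a few programming conditions and one listing, with no new data. Some AEs become not determinable. A second dose taken before 2 hours without a record of it could still be misplaced, and AEs between first dose + 2 h and the true second dose on the CRF date remain with the second dose. The listing makes the reassigned events visible.
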